Evaluating the Value of Telehealth for Care of Children With Medical Complexity
Clinicaltrials.gov Identifier: NCT02849938
Unique Protocol ID: CCCMCTeleMed

Study Protocol and Statistical Analysis Plan

Last Revised: September 29, 2016

Participants

This study was designed as a single center, randomized, non-blinded pilot study. Sample size was determined by number of eligible patients enrolled in the Coordinated Care for Children with Medical Complexity (CCCMC) program at our institution as well as number of devices that were available for the pilot. Inclusion criteria included: patients aged 1 month to 18 years, currently enrolled in the CCCMC program; parent consent; at least one English-speaking parent; and in-home Wi-Fi connectivity. Children enrolled in the CCCMC program met the following criteria: 3 or more body systems requiring active management; technology dependent or full support to complete activities of daily living; and moderate or severe neuromotor delays, or intellectual disability. Children were excluded from this pilot study if caregivers expressed an inability to comply with study requirements. Participants were randomized 1.5:1 with stratification based on tracheostomy status to control group or intervention group (Research Randomizer, Urbaniak). This stratification was done to attempt to balance patient contact between the groups based on the assumption that patients with tracheostomies may require more frequent contact with the CCCMC team. Clinicians in the CCCMC program included a pediatrician and pediatric nurse practitioner. This study and subsequent revision was approved by the Advocate Health Care Institutional Review Board and registered at ClinicalTrials.gov (Identifier: NCT02849938).

Telehealth Device

The selected telehealth device (TytoHome™) is an FDA-approved, handheld, mobile device designed for capture and transmission of ear, throat, and skin images, heart and lung auscultations including heart rate detection, and temperature data taken by infrared transdermal thermometer. The device required pairing with an iOS tablet (Apple iPad mini 4) for transmission via wireless network for live-interactive clinician connection. Caregivers used the telehealth device to perform non-invasive medical examinations in the home for remote view by a clinician. TytoCare™ provided the telehealth devices and the iPad minis that were used in the pilot.

Procedure

Enrolled parent caregivers provided informed consent during a home visit for study initiation. For those in the intervention group, members of the TytoCare™ team were present along with study team to explain the use of the telehealth device and iPad mini; set up the components and connect them to in-home Wi-Fi; and answer any questions. The home was assessed for adequate internet connectivity and supplemental connectivity was provided by TytoCare™ if needed.

All caregivers were instructed to contact their clinician by telephone or email as usual when they had any health concerns. If an exam was deemed necessary by the clinician, patients in the control group were referred for an in person encounter, whereas caregivers of patients in the intervention group were directed to connect the telehealth device if appropriate. During a telehealth visit, the clinician conducted a 2-way, live, interactive

audio/video visit with the patient. If clinically indicated the clinician would direct the caregiver to use the telehealth device to provide temperature, lung sounds, heart sounds, oropharyngeal exam, skin exam and/or ear exam. Regardless of the group, the clinician would base direction for necessary treatment, referral to an ED, clinic visit or hospitalization based on available data. In addition, telehealth visits were scheduled in advance for routine care if indicated such as for post-discharge care, follow-up for a particular concern, or to maintain familiarity with the telehealth device (technical practice).

Data Collection

The length of the study observation period was increased from 3 to 4 months due to technology issues that were encountered and managed during the first month of the study (termed “technical month”). Data collection included subject demographics, encounter details (outpatient clinic visits, ED visits, and hospitalizations) that were routinely collected as a part of the CCCMC program, as well as caregiver and clinician surveys, which used a 4-point Likert response scale. All caregivers answered questions about CCCMC program satisfaction, and those in the intervention group answered additional questions about their comfort using the device. Caregivers were emailed a link to the online survey once a month during the study period. Surveys not completed online were conducted over the phone by a member of the study team who did not participate in patient care. Clinicians completed an online survey for each encounter in which they would have liked to complete a telemedicine visit regardless of child’s group assignment. They answered general satisfaction questions as well as demographic, feasibility, and

usability questions. Questions on the feasibility and usability of the telehealth device addressed the success of device connectivity, as well as the transmission of real-time images, temperature, and sound. Other questions asked about potential or actual changes in patient management because of the telehealth device. Specific measures to address each study outcome can be found in Table 1.

Analysis

Descriptive statistics were used to summarize data with absolute and relative frequencies for categorical variables and means and standard deviations (SD) for continuous variables. Feasibility and usability of the device as determined from survey responses and reported as median and interquartile range (IQR). Continuous variables were examined using independent groups Student's t-test or the Mann-Whitney U test depending upon normality of data. Dichotomous variables were examined using Chi-square or Fisher exact tests. Data are reported for the first technical month and subsequent 3-month observation period separately.

The impact of device utilization was evaluated by measuring the total number of visits per patient by type (outpatient visits of low, moderate, and high complexity; ED visit without subsequent admission, general pediatric ward days, pediatric intensive care unit days) as determined via chart review. To adjust for the difference in sample size per group, the number of hospitalization days, acute office visits, and ED visits were reported descriptively as a *visit rate* calculated as the number of visits or hospital days/patient study months (number of patients in the group x number of study months). Four months of data were used for the calculation because the control group did not have any

hospitalizations during the technical month. The Kaplan-Meier method was used to estimate the proportion of each group that did not have any hospitalizations during the study period. A statistical comparison of the survival distribution was not conducted because the Kaplan-Meier method does not account for repeated episodes such as patients with more than one hospitalization.

A negative binomial regression model with Generalized Estimating Equations to handle repeated measurements was used to test the difference in hospital length of stay between groups. Model results were reported as regression coefficients, 95% Wald confidence intervals and p values. The negative binomial regression model was appropriate for this analysis, as the distribution of the outcome had greater variability than expected under a Poisson distribution. The sample mean of the outcome (4.3) was substantially smaller than its variance (102.3). Regression models were not tested for the number of acute office or ED visits because the incidence rate was too small for the inferential statistic. Analyses were conducted using SPSS (version 22.0) (IBM Corp. Released 2013. IBM SPSS Statistics for Windows, Version 22.0. Armonk, NY: IBM Corp). For all analyses, a p value < 0.05 was considered statistically significant.

Direct cost for each encounter was obtained from our institution's financial accounting system (EPSi), which was used to calculate direct costs per study group and encounter type (not including overhead costs such as cost of the telehealth device or connectivity). For the intervention group, a telemedicine visit was equated to a Level 4 return encounter in the outpatient setting. Direct cost savings were calculated as the absolute difference between the two study groups. To adjust for the difference in group sample size, the

encounter direct cost was multiplied by the visit rate and the adjusted cost rates were described for each group. Potential cost savings were calculated using clinician input on the visit types that were likely prevented as a result of the telemedicine device.

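### Device feasibility is summarised only by median and IQR, which can read as a perfect score while a meaningful minority of connections or transmissions fail

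*Combined protocol and SAP*

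**What the plan says.** The Data Collection section describes "caregiver and clinician surveys, which used a 4-point Likert response scale". It says that the feasibility and usability questions "addressed the success of device connectivity, as well as the transmission of real-time images, temperature, and sound". The unit of the clinician survey is the encounter: "Clinicians completed an online survey for each encounter in which they would have liked to complete a telemedicine visit", in either study group.

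The Analysis section opens with a general rule: "Descriptive statistics were used to summarize data with absolute and relative frequencies for categorical variables". The next sentence is specific to the device: "Feasibility and usability of the device as determined from survey responses and reported as median and interquartile range (IQR". The same paragraph adds: "Data are reported for the first technical month and subsequent 3-month observation period separately".

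The available text gives no success proportion, failure count, denominator of attempts or feasibility threshold. It also gives no item wording, score coding or number of encounters. Data Collection refers to Table 1 for the specific measures, and that table is not in the text available for review.

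**The concern.** Whether a connection was made or a sound file arrived is naturally a question of how often it worked. A median with IQR reports three percentiles. On a scale with only four values and most answers at the top, all three can equal the top value while a sizeable minority of uses go badly.

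This matters because the study is a pilot and was lengthened from 3 to 4 months after technology problems in its opening month. A reader will want to know how often each function failed, and whether that changed after the technical month. A row of identical 4 (4-4) entries could not answer either question.

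**Working it through.** The plan states no figure to reproduce, so the check is of what the stated summary can and cannot show.

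**Inputs.** From the documents: a four-point scale, median and IQR as the summary, and SPSS as the software ("Analyses were conducted using SPSS (version 22.0"). Assumed: answers coded 1 to 4 with 4 best; failures scored 1 and successes 4; quartiles by the weighted average at position (n+1)p; n from 8 to 200 surveys, because no count is given.

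**Formula.** Sort n answers, of which f are failures. The lower quartile sits at position h = (n+1)/4. It equals 4 only if the answer at position floor(h) is already a 4, that is, if f ≤ floor((n+1)/4) − 1. Median and upper quartile are then 4 as well. Since (n+1)/4 − 1 = (n−3)/4 < n/4, the hidden share is always below 25%.

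**Largest number of failures still shown as 4 (4-4):**

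| n | floor((n+1)/4) − 1 | share |
|---|---|---|
| 8 | 1 | 12.5% |
| 10 | 1 | 10% |
| 12 | 2 | 16.7% |
| 16 | 3 | 18.8% |
| 20 | 4 | 20% |
| 40 | 9 | 22.5% |
| 60 | 14 | 23.3% |
| 100 | 24 | 24% |
| 200 | 49 | 24.5% |

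Four other quartile definitions gave the same or a slightly higher share (up to 20% at n = 10, 23.3% at n = 30 and 24% at n = 50), always below 25%.

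**Where it moves.** At n = 40 with f = 10, h = 10.25, so the lower quartile is 1 + 0.25 × (4 − 1) = 1.75. At f = 9 it is still 4.

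**What counts would show.** Exact (Clopper-Pearson) 95% limits are the 0.025 quantile of Beta(k, n−k+1), taken as 0 when k = 0, and the 0.975 quantile of Beta(k+1, n−k). For n = 40:

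- 0 failures: 0% (0 to 8.8%)
- 8 failures: 20% (9.1 to 35.6%)
- 9 failures: 22.5% (10.8 to 38.5%)

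All three read 4 (4-4) under the planned summary. With 20 surveys, 4 failures are 20% (5.7 to 43.7%) and also read 4 (4-4). These intervals treat uses as independent.

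**How often this would happen.** If the true failure rate were 20% and uses were independent, the chance of a 4 (4-4) display is P(F ≤ f_max) with F ~ Bin(n, 0.20). This is 63% at n = 20, 73% at n = 40 and 87% at n = 100.

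**The case against.** The strongest reply is that the items cannot be seen. If Table 1 or the survey uses yes/no items, the general rule on frequencies arguably covers them. If the items are graded ratings, median and IQR is a conventional ordinal summary, and a score below the top need not mean failure. This stands as a limit on confidence. It does not remove the point: the one sentence about feasibility and usability follows the general rule and names only median and IQR.

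The illustration is also a constructed case, with answers only at 1 or 4. Any spread into the middle categories counts towards the quarter that moves the lower quartile, so fewer failures could be hidden behind 4 (4-4).

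Two stronger readings are tempting, and the documents do not support them:

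- *The summary can never tell a perfect device from one failing in one use in five.* With 10 surveys and the assumed quartile rule, 2 failures put the lower quartile at position 2.75, giving 1 + 0.75 × 3 = 3.25, which is visible. Separate reporting of the technical month makes each n smaller still.
- *A bad sensor disappears into a pooled score.* Connectivity, images, temperature and sound are listed as separate topics and nothing says they are pooled. A function failing clearly more than a quarter of the time would show in its own lower quartile.

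Finally, this is descriptive reporting in a pilot with no stated go/no-go threshold, and no test or group comparison depends on it. That is fair and keeps the point modest.

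**Conclusion.** The point holds as a reporting weakness. Under the stated summary, a display of 4 (4-4) is compatible with failures in about 10-20% of uses when there are 8 to 20 surveys. With many surveys the share approaches 25% without reaching it. This rests on three assumptions: 4 is the best score, failures fall below it, and nearly all other answers are at the top. The encounter count and coding are not given, so the size for this trial is unknown.

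A reader might infer that nearly a quarter of uses failed unseen. That figure is the limit for large numbers of surveys, and the documents do not show that any failures were hidden. Nor do they support treating the bottom two categories as failure. Confidence is moderate. The change is worth making because it is cheap and bears directly on what the pilot can say about feasibility.

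**What to change.** Add to the feasibility sentence in the Analysis section that, for each function (connection, images, temperature, sound), the count and percentage in each of the four response categories will be reported, with median and IQR as a supplement.

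- **Denominator.** Use encounters in which that function was actually attempted. Clinician surveys also cover control-group encounters, and the Procedure section has individual examinations done only as clinical need arose, so both control encounters and unused functions must be excluded.
- **Periods.** Give the table separately for the technical month and the following 3 months, a split that the plan already makes.
- **Failure.** If a single failure proportion is wanted, define it from the actual item wording.
- **Intervals.** Any interval should allow for repeated uses by the same child, or be labelled approximate. Exact binomial limits ignore that repetition.

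The cost is a short change of wording and one extra table. The response counts come from survey data already collected. The denominators also require that the survey or encounter record shows which functions were attempted, which should be confirmed. The results may look less favourable than a row of perfect medians.

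### With arms randomized 1.5:1, letting a normality check choose between Student's t-test and Mann-Whitney does not hold 5% for a difference in means if spread differs between arms

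*Combined protocol and SAP*

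**What the plan says.** The combined protocol and SAP gives one general rule in its Analysis section: continuous variables are tested by Student's "t-test or the Mann-Whitney U test depending upon normality of data". It names no normality test, no cut-off, no check of variances and no list of the variables covered. The same section gives "means and standard deviations (SD) for continuous variables" as the summary.

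The Participants section sets the allocation: "Participants were randomized 1.5:1 with stratification based on tracheostomy status to control group or intervention group". Read in word order, control is the larger arm. No number of patients is stated; "Sample size was determined by number of eligible patients enrolled" and by the devices available.

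The threshold is general: "For all analyses, a p value < 0.05 was considered statistically significant". Sidedness is not stated.

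Two groups of outcomes are handled elsewhere. A negative binomial GEE model "was used to test the difference in hospital length of stay between groups". Rates of hospital days, office visits and ED visits, and the cost rates built on them, are described without a test.

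**The concern.** There are two separate weaknesses.

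- **Unequal arms.** Student's test with a pooled variance tolerates unequal variances well when the arms are the same size. At 1.5:1 the pooled variance leans towards the larger arm. The standard error is then too small if the smaller arm is the more variable, and too large if the larger arm is. A normality check looks at shape and gives no protection against this.
- **A hypothesis chosen by the data.** If the check passes, means are compared; if it fails, ranks are. Mann-Whitney can be significant when the two means are equal, so a p value printed beside a mean and SD may not refer to the mean. With no criterion named, the choice of test can also be made after the data are seen.

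At stake is whether a reader can take p < 0.05 on a continuous variable as a 5% test of a difference in means.

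**Working it through.** **Inputs from the document:** the test rule, the 1.5:1 allocation and the 0.05 threshold. There is no planned power or sample size to reproduce.

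**Assumptions:** two-sided test; control:intervention sizes 12:8, 15:10, 30:20 and 60:40; r = SD(intervention)/SD(control) from 0.5 to 2 in simulation and up to 4 in the formula; Student's means pooled variance; the normality check is Shapiro-Wilk at 5% in each arm.

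**Step 1. Large-sample error of the pooled test.** Take relative sizes 1.5 (control) and 1 (intervention), and control SD 1.

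- True variance of the difference: V_true = 1/1.5 + r².
- Variance the pooled test assumes: V_pooled = [(1.5 + r²)/2.5] × (1/1.5 + 1).
- Error = 2 × [1 − Φ(1.96 × √(V_pooled/V_true))].

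For r = 2: V_true = 0.667 + 4 = 4.667; V_pooled = 2.2 × 1.667 = 3.667; ratio 0.786; 1.96 × 0.886 = 1.737; error 8.2%.

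For r = 0.5: V_true = 0.667 + 0.25 = 0.917; V_pooled = 0.7 × 1.667 = 1.167; ratio 1.273; 1.96 × 1.128 = 2.211; error 2.7%.

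The same formula gives 3.4% at r = 0.67, 5.0% at r = 1, 7.0% at r = 1.5 and 10.1% at r = 4. With 1:1 arms it gives 5.0% at every r, so the allocation is what opens the gap. A larger sample does not close it.

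**Step 2. Simulation, normal data, equal means.** 4,000 trials per setting; Monte Carlo standard error √(0.05 × 0.95/4000) ≈ 0.3 points. Ranges run over the four sizes.

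| r | Student's t alone | Two-stage rule | Welch |
|---|---|---|---|
| 2 | 8.4–8.6% | 8.7–8.8% | 4.8–5.0% |
| 1.5 | 6.7–7.3% | 6.8–7.4% | 4.9–5.2% |
| 1 | 4.6–5.4% | 4.6–5.9% | 4.5–5.1% |
| 0.67 | 3.2–4.1% | 3.4–4.3% | 4.7–5.9% |
| 0.5 | 2.3–3.5% | 2.5–3.8% | 4.3–5.4% |

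The check sent about 9–11% of these normal data sets to Mann-Whitney whatever the SD ratio. Two 5% checks on normal data fail at 1 − 0.95² = 9.75%, so the switching is chance and carries no information about spread.

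**Step 3. Skewed data (lognormal and gamma).**

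- Identical distributions (lognormal): two-stage rule 4.9–5.4%; Welch 2.7–4.5%.
- Equal means, unequal spread: two-stage rule 14.9–63.4%, rising with size; Mann-Whitney alone 14.6–63.4%; Welch 4.8–10.6%. The rule switched to Mann-Whitney in 72–100% of trials.

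The first two ranges in the last line are almost the same. The rejections come from the rank test responding to distributions that really do differ.

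**Step 4. Price of Welch when variances are equal.** With a true difference of one SD, power goes from 54.3% to 53.0% at 12:8 and from 85.5% to 85.1% at 24:16.

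**The case against.** The strongest reply is that randomization makes the two distributions identical if the device does nothing, and the rule then holds its level: 4.6–5.9% in every such setting above. This stands. The error departs from 5% only for a hypothesis of equal means with unequal spread or shape, and the document never names a difference in means as its target; it only lists means and SDs as the summary.

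The scenarios are also assumed. At an SD ratio of 1.25 the two-stage rule gives only 5.8–6.2% on normal data. No SD by arm is reported. The only distribution figures, a mean of 4.3 and a variance of 102.3, are for length of stay and are not split by arm. This stands too, and it limits what can be said about size.

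A reader might infer that p values on visit counts or costs are affected. The document does not support that: those rates are descriptive, and length of stay has its own model. The rule could cover continuous demographics, survey scores or per-patient counts. Which of these is not stated, and Table 1 is not in the text available for review.

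A reader might also take the 14.9–63.4% for skewed data as inflated false positives. It mostly shows Mann-Whitney detecting a real difference in distribution. The fair criticism there is that the question changes with the data.

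What the reply does not remove is that the rule gives no protection against unequal spread in arms made unequal by design, and that it leaves the hypothesis to an unspecified check.

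**Conclusion.** The point holds conditionally and is minor. For continuous variables tested by this rule, 5% is not assured for a difference in means when spread differs between 1.5:1 arms. With a twofold SD ratio the error is about 8–9% if the smaller arm is the more variable and about 3% if the larger arm is, against about 5% for Welch. If the 1.5 share belongs to the intervention arm, the same statement holds with the arms exchanged.

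The figures rest on assumed arm sizes and SD ratios, a Shapiro-Wilk check, a two-sided test and the usual meaning of Student's. The actual error in this trial cannot be computed. The unconditional reading, that the rule fails its 5% level whatever the data, is not supported. In a pilot with no primary outcome tied to the rule, this calls for a clearer sentence and does not put the trial's conclusions in doubt.

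**What to change.** Replace the sentence in the Analysis section by:

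*Continuous variables summarized by means are compared with Welch's unequal-variance t-test and a 95% confidence interval for the difference; 4-point survey items are compared with the Mann-Whitney test, reported as a comparison of ranks; the test is fixed by type of variable, not by a normality check.*

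The survey part fits the existing choice of median and IQR for feasibility and usability. No new test is needed for visit or cost rates, since the plan gives them none.

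Costs:

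- About 1–2 points of power when variances are equal.
- A re-run of the affected tests if they have already been done. The document is written in the past tense and reports outcome figures, so such a re-run should be labelled as a later change.
- Welch is only approximate in small skewed samples: about 5–9% in gamma scenarios at 12:8 and 24:16, up to 10.6% in the wider set above, and below 5% (down to 2.7%) for identical lognormal data. It removes the unequal-SD problem for roughly normal data; it does not guarantee exactly 5% everywhere.

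### Telehealth visits are priced but have no stated count or visit rate, so office visits they replace can read as reduced use and lower adjusted cost

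*Combined protocol and SAP*

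**What the plan says.** **Who gets which visit (Procedure).** Caregivers in both arms contact the clinician in the usual way. If the clinician thinks an examination is needed, control patients are seen in person and intervention caregivers are told to connect the device where that is appropriate. Telehealth visits can also be booked ahead, for example after discharge, for follow-up, "or to maintain familiarity with the telehealth device (technical practice").

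**What is counted (Analysis).** The device's impact is measured by total visits per patient of these types: "outpatient visits of low, moderate, and high complexity; ED visit without subsequent admission, general pediatric ward days, pediatric intensive care unit days".

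**What gets a rate (Analysis).** To allow for unequal group sizes, "the number of hospitalization days, acute office visits, and ED visits were reported descriptively" as a visit rate, that is, events divided by patients times study months. "Four months of data were used for the calculation".

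**What is costed (Analysis, direct-cost paragraph).** For the intervention group, "a telemedicine visit was equated to a Level 4 return encounter in the outpatient setting". The size-adjusted figure is then formed as follows: "encounter direct cost was multiplied by the visit rate and the adjusted cost rates were described for each group".

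**The concern.** The same clinical need can produce an office visit in one arm and a telehealth visit in the other. If only the office visit is counted, a lower office rate in the intervention arm cannot separate children who needed fewer examinations from children who were examined by another route. A study of the value of telehealth has to make that distinction.

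The cost side matters as much. Allocation is 1.5:1, so unadjusted group totals are not directly comparable: if that ratio is achieved and cost per patient is equal, the larger group's total is 1.5 times the smaller's. The size-adjusted cost is therefore the figure a reader will compare. It is also the one for which the plan states no telehealth rate. The unadjusted cost can include telehealth visits at the Level 4 price, so the two cost figures may rest on different sets of visits.

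**Working it through.** There is no figure in the plan to reproduce: it gives no group sizes, visit counts, visit rates or unit costs. The check is a comparison of the lists, followed by algebra on assumed inputs.

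**Step 1. Where telehealth appears.**

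| Place | Content | Telehealth named? |
|---|---|---|
| Data Collection, encounter details | Clinic, ED and hospital encounters | No |
| Analysis, visits per patient by type | Outpatient by complexity, ED without admission, ward days, PICU days | No |
| Analysis, visit rate | Hospital days, acute office visits, ED visits | No |
| Analysis, direct cost: unit price | Level 4 outpatient return visit | Yes |
| Analysis, direct cost: size-adjusted | Encounter cost × visit rate | No rate stated |

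The term needed for the intervention arm is Level 4 cost × telehealth visits per patient-month. The first factor is defined and the second is not.

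**Step 2. What this does to the comparison.** Assume:

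- *r*: examinations needed per patient-month outside hospital and ED, the same in both arms;
- *f*: fraction of these moved from office to device in the intervention arm;
- *s*: additional scheduled telehealth visits per patient-month;
- office and telehealth visits each priced at one Level 4 unit.

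As listed, the control rate is *r* and the intervention rate is *r*(1 − *f*). The rate ratio is 1 − *f* and the apparent saving is *r* × *f*.

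With a telehealth rate of *rf* + *s* added, the intervention total is *r*(1 − *f*) + *rf* + *s* = *r* + *s*. The rate ratio is 1 + *s*/*r* and the saving is −*s*.

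**Step 3. Assumed values.** Savings are in Level 4 units per patient-month.

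| *r* | *f* | Ratio as listed | Saving as listed | Ratio with telehealth, *s* = 0 | Ratio with telehealth, *s* = 0.25 |
|---|---|---|---|---|---|
| 0.1 | 0.25 | 0.75 | 0.025 | 1.00 | 3.50 |
| 0.1 | 0.75 | 0.25 | 0.075 | 1.00 | 3.50 |
| 0.3 | 0.50 | 0.50 | 0.150 | 1.00 | 1.83 |
| 0.5 | 0.25 | 0.75 | 0.125 | 1.00 | 1.50 |
| 0.5 | 0.75 | 0.25 | 0.375 | 1.00 | 1.50 |

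With telehealth included, the saving is 0 when *s* = 0 and −0.25 when *s* = 0.25, whatever *r* and *f* are.

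These numbers show the direction and mechanism only. The ratio as listed restates the assumed *f*, and the last column restates the assumed *s*/*r*. None is an estimate for this trial.

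**The case against.** The strongest reply is that telehealth is already folded in. The direct-cost paragraph works by study group and encounter type, equates a telehealth visit with an outpatient visit, and then multiplies encounter cost by the visit rate. The list of outpatient visits by complexity is not limited to acute or in-person visits. On that reading a telehealth visit is simply an outpatient encounter.

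This is possible for the per-patient totals, but the equating sentence is a costing rule, not a counting rule. It also does not carry over to the rate, which covers acute office visits: scheduled follow-up, post-discharge and practice sessions do not fit that label. If telehealth visits were folded in silently, in-person and remote visits could no longer be told apart.

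Four further points stand and limit the concern:

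- Table 1, where the Data Collection section places the specific measures, is not in the text. It may list telehealth counts.
- The affected quantities are descriptive, and the Analysis section says office and ED visits were too infrequent to model. The absolute cost effect may be modest.
- Fewer in-person visits is a legitimate outcome for a telehealth pilot. The in-person rate should stay; it needs a companion.
- A reader might infer that practice sessions were charged at Level 4 and inflate the intervention arm's unadjusted cost. The text does not establish this. It neither says that practice sessions were costed nor that they had no clinical content. It only leaves their treatment open.

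**Conclusion.** The gap is real on the text as written. Telehealth has a unit cost but no stated visit type and no rate, so the size-adjusted cost has no telehealth rate to multiply. To the extent that telehealth replaces office visits, the intervention arm's office rate and adjusted outpatient cost fall even if total clinician encounters do not.

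A reader might go further and infer that the fall is guaranteed by construction. It is not: the device is used only where appropriate, and the clinician can still refer a child in either arm to clinic or ED. Nor can one infer that telehealth is missing from costing altogether, since the unadjusted cost can include it at the Level 4 price.

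The size cannot be given, because the plan reports no telehealth or office counts and no costs. The conclusion assumes that Table 1 does not define a telehealth count or rate. Hospital days and the length-of-stay model are not affected by this gap. It should be corrected because it bears on the study's main question, but it does not undermine the one modelled outcome.

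**What to change.** In the Analysis section, where visit types and the visit rate are defined:

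- add telehealth visits as a counted type with their own rate per patient-month;
- report in-person plus telehealth encounters combined, by arm, beside the in-person rate.

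In the direct-cost paragraph:

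- add telehealth rate × Level 4 cost to the intervention arm's adjusted cost;
- use the same set of visits for the unadjusted and adjusted costs;
- identify technical-practice sessions and show them on a separate line, so that a reader can see the result with and without them.

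The cost is some plan wording, one extra row in the utilisation and cost tables, and a label on each telehealth visit. The Data Collection section does not list telehealth among the routinely collected encounters, but pricing telehealth visits already requires counting them. No new patients, procedures or tests are needed. The downside for the study team is a smaller apparent reduction in outpatient use and adjusted cost.
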